## 8. STATISTICAL ANALYSIS PLAN

### 8.1 GENERAL CONSIDERATIONS

The statistical analysis of the data will be performed by Inovio Pharmaceuticals or its representative.

This is a two-arm, multi-center, open-label randomized clinical trial of VGX-3100 and VGX-3100 with imiquimod, in subjects with a histologic diagnosis vulvar HSIL and confirmed vulvar infection with HPV types 16 and/or 18. The study's primary endpoint is binary: regression of vulvar HSIL and viral clearance of HPV-16 and/or HPV-18 from vulvar tissue based on tissue collected at Week 48. The primary hypothesis is that each of the treatment arms will result in regression of HSIL and clearance. Secondary efficacy analyses pertain to regression, clearance of HPV-16 and/or HPV-18 infection, regression to normal, non-progression, and anatomic extent. Other secondary analyses concern safety and humoral and cellular immunological measures. Exploratory efficacy analyses concern extended dosing with respect to regression, clearance, and anatomic extent, clearance outside of the vulva, and effect of HLA type on efficacy. Other exploratory analyses pertain to tissue immunological measures and patient-reported outcomes.

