## 8.9 EFFICACY ANALYSIS

The true treatment effect on the primary endpoint is  $p$ , where  $p$  denotes the true population probability of the primary endpoint for each arm. The primary hypothesis of superiority is:

$H_0: p \leq 0.02$  vs.  $H_1: p > 0.02$ , for each treatment arm separately.

A p-value for these hypothesis tests and corresponding 95% confidence intervals will be computed based on the exact method of Clopper-Pearson. Superiority will be concluded if the one-sided p-value is  $< 0.025$  and the corresponding lower bound of the 95% CI exceeds 0.02.

The secondary efficacy binary endpoints will be analyzed in the same manner as the primary hypothesis, but without the hypothesis test p-values.

For the analyses, the efficacy time frame is defined by any time starting from 14 days prior to the -specified visit week.

The anatomic extent endpoint will be analyzed by calculating the mean percent change and associated 95% t-distribution based confidence interval. The percentage of subjects with no clinically significant lesion resolution (reduction in lesion size of 25% or less), partial lesion resolution (26-99% reduction), and complete reduction (100% reduction) will be summarized with point estimates and associated exact Clopper-Pearson 95% confidence intervals.

An exploratory analysis will examine clearance outside of the vulva. This will be analyzed in the same manner as vulvar clearance.

An exploratory analysis will examine the relationship between the primary efficacy endpoint and a) HLA results, b) miRNA results, c) vulvoscopy results, and d) HPV results. Relationships will be examined with contingency tables and/or logistic regression models which model the primary endpoint versus these results and treatment group as regressor variables.

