 Throughout this protocol high grade disease (previously known as VIN2 or VIN3) is referred to as vulvar HSIL according to the 2015 International Society for the Study of Vulvovaginal Disease (ISSVD) Terminology of Vulvar Squamous Intraepithelial Lesions and 2012 consensus recommendation on Lower Anogenital Squamous Terminology (LAST) from the American Society of Colposcopy and Cervical Pathology (ASCCP) and the College of American Pathologists (CAP).

 Inclusive of administration on day of dosing.

 No evidence of vulvar HSIL is defined as normal tissue or vulvar LSIL (VIN 1) or condyloma

 A treatment responder is defined as a subject with no histologic evidence of vulvar HSIL and no evidence of HPV-16 or HPV-18 in vulvar tissue at evaluation and who did not receive any non-study related treatment for vulvar HSIL. A treatment non-responder is defined as a subject with histologic evidence of vulvar HSIL, or vulvar carcinoma at evaluation, or a subject with evidence of HPV-16/18 in vulvar tissue at evaluation, or a subject who received non-study related treatment for vulvar HSIL.

Secondary Objectives	Associated Secondary Endpoints
1. Evaluate the safety and tolerability of VGX-3100 delivered IM followed by EP with CELLECTRA™ 2000, alone or in combination with imiquimod	1a. Local and systemic events for 7 days following each dose as noted in the Participant Diary. 1b. All adverse events including SAEs, SUSARs, UADEs, and other unexpected AEs for the duration of the study (through Week 100 visit)
2. Determine the efficacy of four doses of VGX-3100, alone or in combination with imiquimod, as measured by histologic regression of vulvar HSIL	2. Proportion of subjects with no evidence of vulvar HSIL  on histology (i.e. biopsies or excisional treatment) at Week 48 visit
3. Determine the efficacy of four doses of VGX-3100, alone or in combination with imiquimod, as measured by virologic clearance of HPV-16/18 in vulvar tissue	3. Proportion of subjects with no evidence of HPV-16/18  in vulvar tissue samples at Week 48 visit

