5. Describe virologic clearance of HPV-16/18 from non-vulvar anatomic locations	5. Proportion of subjects who have cleared HPV-16/18 on specimens from non-vulvar anatomic locations without surgical intervention (inclusive of cervix, oropharynx, vagina and intra-anus) at Week 48 compared to baseline
6. Characterize HLA haplotypes and the correlation with efficacy	6. Proportion of subjects with regression of HSIL on histology (i.e. biopsies or excisional treatment) at Week 48 visit
7. Describe association of microRNA (miRNA) profile, previous vulvoscopy, and HPV testing results with Week 48 histologic regression	7. Vulvoscopy, HPV test results (vulvar swab and vulvar tissue) and miRNA profile (Day 0, Week 15 and 48) in conjunction with histologic regression of vulvar HSIL at Week 48 visit

 Baseline photographic imaging is defined as photographs obtained at Day 0 prior to the first study dose. Digital photos will be analyzed with a computer program to calculate the total lesion size in cm^2.

 Additional assessments may include visualization of PD-L1, Granulysin, perforin, CD137, CD103 and possibly other relevant markers identified in the literature in vulvar tissue as sample allows.

8. Describe patient reported outcomes (PRO) for subjects treated with VGX-3100 and VGX-3100 with imiquimod	8. PRO endpoints will be obtained at Day 0 prior to first dose, Weeks 4, 12, 24 after dosing, and at Weeks 15, 27, 48, 52, 74, 96, and 100.
--	---

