- 1) Untreated microinvasive or invasive cancer;
- 2) Biopsy-proven Vaginal Intraepithelial Neoplasia (VAIN) and are not undergoing medical care and/or treatment for VAIN;
- 3) Biopsy-proven Anal Intraepithelial Neoplasia (AIN) and are not undergoing medical care and/or treatment for AIN;
- 4) Biopsy-proven Cervical Intraepithelial Neoplasia (CIN) 2/3 and are not undergoing medical care and/or treatment for CIN;
- 5) Biopsy-proven differentiated VIN;
- 6) Vulvar HSIL that is not accessible for sampling by biopsy instrument;
- 7) Vulvar HSIL that is not of adequate size to ensure that a visible lesion remains after biopsy;
- 8) Treatment for genital warts within 4 weeks prior to screening;
- 9) Any previous treatment for vulvar HSIL (e.g. with surgery and/or imiquimod) within 4 weeks prior to screening;
- 10) Allergy to imiquimod 5% cream or to an inactive ingredient in imiquimod 5% cream;
- 11) Is pregnant, breastfeeding or considering becoming pregnant within 6 months following the last dose of investigational product;
- 12) Presence of any abnormal clinical laboratory values greater than Grade 1 per Common Toxicity Criteria for Adverse Events (CTCAE) v 4.03 within 45 days prior to Day 0 **or** less than Grade 1 but deemed clinically significant by the Investigator;
- 13) Immunosuppression as a result of underlying illness or treatment including:
  - a) History of or positive serologic test for HIV at screening;
  - b) Primary immunodeficiencies;
  - c) Long term use ( $\geq 7$  days) of oral or parenteral glucocorticoids at a dose of  $\geq 20$  mg/day of prednisone equivalent (use of inhaled, nasal, otic, and ophthalmic corticosteroids are allowed);
  - d) Current or anticipated use of disease modifying doses of anti-rheumatic drugs (e.g., azathioprine, cyclophosphamide, cyclosporine, methotrexate) and biologic disease modifying drugs such as TNF- $\alpha$  inhibitors (e.g. infliximab, adalimumab or etanercept);
  - e) History of solid organ or bone marrow transplantation;
  - f) Any prior history of other clinically significant immunosuppressive or clinically diagnosed autoimmune disease that may jeopardize the safety of the subject or require therapy that would interfere with study assessments or endpoint evaluation, or otherwise impact the validity of the study results.
- 14) History of previous therapeutic HPV vaccination (licensed prophylactic HPV vaccines are allowed, e.g. Gardasil®9, Gardasil®, Cervarix®);

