## 2.3 EXPLORATORY OBJECTIVES AND ASSOCIATED ENDPOINTS

Exploratory Objectives	Associated Exploratory Endpoints
1. Describe the efficacy of VGX-3100, administered alone or in combination with imiquimod, at Week 74 and/or Week 96 as measured by reduction in the surface area of the qualifying  vulvar lesion(s), in subjects without a complete resolution at Week 48	1. Percent reduction in the cumulative surface area of the acetowhite vulvar lesion(s) as determined by the quantitative analysis of standardized pre-biopsy photographic imaging of the qualifying  lesion (s) at Week 74 and/or Week 96 compared to baseline  . Results will be classified as: no clinically significant lesion resolution (reduction in lesion area of 0-25%), partial lesion area resolution (>25% and <100% reduction), and complete lesion resolution (no visible lesion).
2. Describe the efficacy of 5 or 6 doses of VGX-3100, alone or in combination with prior imiquimod, as measured by histologic regression of vulvar HSIL	2. Proportion of subjects with no evidence of vulvar HSIL on histology (i.e. biopsies or excisional treatment) at Week 74 for subjects who receive 5 doses of VGX-3100 and at Week 96 for subjects who receive 6 doses of VGX-3100.
3. Describe the efficacy of 5 or 6 doses of VGX-3100, alone or in combination with prior imiquimod, as measured by virologic clearance of HPV-16/18	3. Proportion of subjects with no evidence of HPV-16/18 in vulvar tissue samples at Week 74 and/or Week 96.
4. Evaluate tissue immune responses to VGX-3100, and VGX-3100 with imiquimod, as measured in vulvar tissue samples	4. Assessment of pro-inflammatory and immunosuppressive elements in tissue 
5. Describe virologic clearance of HPV-16/18 from non-vulvar anatomic locations	5. Proportion of subjects who have cleared HPV-16/18 on specimens from non-vulvar anatomic locations without surgical intervention (inclusive of cervix, oropharynx, vagina and intra-anus) at Week 48 compared to baseline
6. Characterize HLA haplotypes and the correlation with efficacy	6. Proportion of subjects with regression of HSIL on histology (i.e. biopsies or excisional treatment) at Week 48 visit

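### Exploratory endpoint 5 rules out non-vulvar HPV-16/18 clearance after surgery, but not after ablative or medical therapy at the sampled site

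*Protocol*

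**What the plan says.** The endpoint is worded alike in the Protocol synopsis and in Section 2.3. The synopsis gives it as "Proportion of subjects who have cleared HPV-16/18 on specimens from non-vulvar anatomic locations without surgical intervention", and Section 2.3 likewise refers to "non-vulvar anatomic locations without surgical intervention". It names cervix, oropharynx, vagina and intra-anus, and compares Week 48 with baseline. It sets no other treatment condition.

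Three exclusion criteria bear on the same anatomy:

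- Exclusion 2: "Biopsy-proven Vaginal Intraepithelial Neoplasia (VAIN) and are not undergoing medical care and/or treatment for VAIN"
- Exclusion 3: "Biopsy-proven Anal Intraepithelial Neoplasia (AIN) and are not undergoing medical care and/or treatment for AIN"
- Exclusion 4: "Biopsy-proven Cervical Intraepithelial Neoplasia (CIN) 2/3 and are not undergoing medical care and/or treatment for CIN"

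For the vulvar primary endpoint, the synopsis makes a non-responder of "a subject who received non-study related treatment for vulvar HSIL". That rule covers every kind of treatment, but only treatment of the vulvar lesion.

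On analysis, Section 8.9 says: "An exploratory analysis will examine clearance outside of the vulva. This will be analyzed in the same manner as vulvar clearance". Section 8.1 places it among the efficacy analyses: "Exploratory efficacy analyses concern extended dosing with respect to regression, clearance, and anatomic extent, clearance outside of the vulva".

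The document holds several protocol versions. The endpoint and exclusions above are in Version 2.1, the latest. The part at hand ends in Section 3 of that version, so Sections 6.15, 6.16, 8.1 and 8.9 are cited from Version 2.0.

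**The concern.** The authors decided that concurrent treatment matters for this endpoint and wrote a condition for it, but the condition names one class of treatment only. Women under treatment for disease of the vagina, anus or cervix may enrol, and three of the four sampled sites are exactly these. If such a woman is HPV-16/18 positive at Day 0, has non-surgical therapy directed at that site and is negative at Week 48, the wording counts her as cleared.

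The non-vulvar clearance proportion is the trial's virologic reading beyond the vulva. Section 1.1.17 argues that the response is systemic and may clear the underlying infection, and a reader will look to this proportion for support. Each arm is small and the trial has no untreated arm, so a few confounded clearances could shift the proportion visibly with nothing in the data to reveal it.

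**Working it through.** The protocol gives no figure for this endpoint, so there is none to reproduce. The check sets the definitions side by side and then sizes one misclassified woman.

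**Step 1. Who may enrol.** Each of Exclusions 2 to 4 joins two conditions: biopsy-proven disease, and not being under care and/or treatment. A woman under treatment fails the second condition and is not excluded.

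**Step 2. Must she stop?** Section 6.16 lists prohibited treatments. The only therapy for an HPV-related lesion on the list is imiquimod for vulvar HSIL in the 4 weeks before screening. Therapy for VAIN, AIN or CIN is not listed.

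**Step 3. Does the endpoint remove her?** Only if the therapy is a surgical intervention. Medical therapy is plainly not. Ablation is unclear: Section 1.1.4 first lists surgical excision, laser ablation and off-label medical therapy as three separate options, then places laser ablation in a list introduced as surgery. The endpoint does not settle which reading applies.

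**Step 4. Does another rule remove her?** The vulvar responder rule reaches only treatment for vulvar HSIL. Section 8.9 carries over the method used for vulvar clearance and adds no rule for therapy at the non-vulvar site. Exclusion 22 lets the Investigator keep out a woman whose condition may affect evaluation of any endpoint, but that is discretionary and acts only at entry.

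The wording as written therefore admits the confounded clearance.

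**Step 5. Size.** Assume the proportion is taken per site among m evaluable women who are HPV-16/18 positive there at Day 0. If k of the women counted as cleared had non-surgical therapy at that site, the reported proportion exceeds the proportion without them by k/m, with m held fixed. The protocol gives neither m nor k. The upper limits for m come from the planned arms of 24 and 12 with 90% evaluable (Section 8.3): 0.9 × 24 = 21.6, about 22, and 0.9 × 12 = 10.8, about 11. These would apply only if every evaluable woman were positive at the site, so smaller values are also shown.

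| m (assumed) | k = 1 | k = 2 |
|---|---|---|
| 22 | 1/22 = 4.5 points | 2/22 = 9.1 points |
| 11 | 1/11 = 9.1 points | 2/11 = 18.2 points |
| 8 | 1/8 = 12.5 points | 2/8 = 25 points |
| 4 | 1/4 = 25 points | 2/4 = 50 points |

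At k = 0 the shift is nil, and nothing in the protocol rules that out.

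**The case against.** The case against is substantial, and most of it limits the weight of the point.

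- **Attribution.** A reader might infer that these clearances are credited to VGX-3100. The documents do not go that far. Exploratory objective 5 only describes clearance and names no product, whereas objectives 1 to 3 speak of the efficacy of VGX-3100. Non-vulvar sites have no null rate, and Section 8.9 reserves p-values for the primary hypothesis. Without an untreated comparator, no wording of the endpoint would let the trial attribute clearance at these sites to the product. The listing under efficacy in Section 8.1 makes the inference understandable but does not establish it.
- **How many women.** The criteria speak of care and/or treatment, which includes surveillance alone, and the summary of changes gives surveillance as the reason for the amended wording. Some treatment will be surgical and already screened out. The cervical criterion concerns CIN 2/3 only, and none of the three concerns the oropharynx. This stands: the affected group may be very small or empty.
- **Mechanism.** The protocol describes no non-surgical therapy for VAIN, AIN or CIN and does not say that such therapy clears HPV-16/18. Section 1.1.8 does foresee ablation or medical therapy on study, but in the context of delayed treatment of vulvar HSIL, so it is weak support. This stands too: the endpoint can include confounded clearances, but the documents do not show that it will.
- **The vulvar rule as precedent.** A primary responder definition need not carry over to a descriptive endpoint, and the fact that an amendment widened the vulvar rule does not make endpoint 5 an error. The vulvar rule is a useful model for a fix, nothing more.
- **A matter for the SAP.** Handling of concomitant therapy is often left there. Here, however, the protocol fixes a treatment condition inside the endpoint, and a SAP that follows it would count the medically treated woman. This objection does not remove the point.

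**Conclusion.** The point holds in a limited form. Exploratory endpoint 5 screens out clearance after surgery but not after medical therapy of the sampled site, and leaves ablation unsettled. Women under treatment for VAIN, AIN or CIN 2/3 may enrol, and that therapy is not prohibited. The descriptive non-vulvar clearance proportion can therefore include clearances confounded by other therapy.

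The number affected is unknown. The per-woman shift of 4.5 to 25 points rests on an assumed 22 down to 4 baseline-positive women at a site and on a per-site denominator, neither of which the protocol states. The endpoint is exploratory and untested, so the primary and secondary conclusions stand. The statements on restrictions and analysis also assume that Sections 6.16 and 8 of Version 2.1 match the Version 2.0 text. This is a wording correction worth making because it is cheap; it does not threaten the trial's main inference.

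**What to change.** In exploratory endpoint 5 (synopsis and Section 2.3), replace the surgical condition with: 'without any non-study treatment (surgical, ablative or medical) directed at HPV-related disease of that site from the baseline specimen to Week 48, including therapy ongoing at Day 0'. Count women so treated as not cleared, parallel to the vulvar responder rule. Also report clearance separately by receipt of such treatment. Naming ablation removes the ambiguity in Section 1.1.4, and including therapy ongoing at Day 0 covers women already under treatment at entry. Therapy completed before Day 0 remains outside the condition and can be flagged in the separate report.

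The cost is one phrase and one descriptive table. Section 6.15 already has medications and procedures recorded, back to 8 weeks before the screening biopsy and during the study, so no new data are needed. The downside is a possibly lower, conservative rate, because a treated woman who would have cleared anyway counts as not cleared; the separate report shows how far that matters. This is an analysis definition only and changes no one's clinical care.

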### Study Design:

HPV-201 is a Phase 2, randomized, open-label efficacy study of VGX-3100 (DNA plasmids encoding E6 and E7 proteins of HPV types 16 and 18) administered by IM injection followed by EP delivered with CELLECTRA™ 2000 alone or in combination with imiquimod in adult women with histologically confirmed vulvar HSIL associated with HPV-16 and/or 18. Approximately 36 subjects will be enrolled. Approximately twenty-four subjects will receive VGX-3100 alone and 12 subjects will receive VGX-3100 and topical imiquimod treatment.

Subjects are randomized in a stratified manner according to (a) recurrent disease at screening (0 vs. 1 or more recurrences), (b) multifocal disease (1 vs. 2 or more lesions at screening), (c) Body Mass Index (BMI) category ( $\leq 25$  vs.  $> 25$  kg/m^2), and (d) age category ( $< 45$  years vs.  $\geq 45$  years).

[figure not shown]
To be eligible for the study, subjects must consent to participate and have a vulvar punch biopsy/biopsies of approximately 4 mm with lesion remaining, and photographs of the acetowhite vulvar lesion(s) at the time of screening. In the case of multifocal disease, the two lesions that potentially contain the most advanced disease, as judged by the Investigator, should be chosen for biopsy using vulvoscopy and documented using standardized high resolution photography with a digital single-lens reflex (SLR) camera. Biopsy slides will be sent to the Pathology Adjudication Committee (PAC) by the central laboratory for evaluation prior to enrollment. In order to be eligible for enrollment, the PAC must assign the diagnosis of vulvar HSIL based on the biopsy sample(s). Subjects must also have a vulvar tissue specimen test positive for HPV genotype 16 and/or 18 to be eligible for participation in the study.

To assess quality of life and related impacts on subjects, patient-reported outcome (PRO) instruments will be provided and will include the Short Form Health Survey version 2 (SF-36v2™) (Optum), the EQ-5D-5L (EuroQol Research Foundation), WOMAN-PRO (WOMen with vulvAr Neoplasia) Clinical Trial Version 2.0 and two additional PRO questions assessing quality of life after surgery or biopsy.

All eligible subjects who consent to participate in the study will receive four to six doses of 6 mg of VGX-3100 administered by IM injection followed by EP. The first dose will be administered as soon as possible following confirmation of the HSIL diagnosis, HPV-16/18 status and all other eligibility criteria, but no more than 10 weeks following collection of the subject's biopsy specimen used for diagnosis by the PAC.

Each dose of VGX-3100 will be administered in a 1 mL volume IM followed immediately by EP with the CELLECTRA™ 2000 device. As shown in [Figure 1](#), study subjects will receive at least 4 doses of VGX-3100 and potentially a 5th and 6th dose depending upon their disposition with regard to histologic and lesion area changes. The first dose will be administered on Day 0, the second at Week 4, the third at Week 12, and the fourth dose will be administered at Week 24. Subjects with no HSIL at Week 48 (Subgroups A and B) will receive 4 doses. Subjects with HSIL at Week 48, who have a reduction in lesion size or no increase in lesion size from baseline (Subgroups C or D), may receive a fifth dose of VGX-3100 administered IM with EP at Week 52 per the judgment of the Investigator. Subjects with HSIL at Week 74, who have a reduction in lesion size or no increase in lesion size from baseline (Subgroups C or D), may receive a sixth dose of VGX-3100 administered IM with EP at Week 78 per the judgment of the Investigator. Subjects in Subgroup E may receive surgical treatment per the judgment of the Investigator. All subjects are scheduled to be followed to Week 100.

